4.3 Effectiveness Analysis Set

Not Applicable

5. General Specifications for Statistical Analyses

5.1 Analysis Software

All statistical analysis will be carried out with SAS Software version 9.4 or more recent version.

5.2 Planned Covariate

In this study, analysis of covariance (ANCOVA) is not planned. All the categorical baseline background factors will be considered in the multiple logistic regression model. Except when noted otherwise, the factors which showed significant difference (p-value <0.05) in the analysis of AE incidence proportion by baseline background factors will be included.

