5.5 Other Statistical Considerations

The analysis will be performed considering the following, and if a separate consideration is required for each analysis item, the content will be described in section in 7.1 Derivation.

- All test statistics will be the results of two-sided test with the statistical significant level of 0.05.
- When calculating percentage in categorical variables in accordance with baseline background factor, the denominator will be defined by total number of subjects in each category. However, the denominator of detail items such as past / current medical history, Cervarix vaccination history, prior / concomitant medication, prior / concomitant vaccination will be defined by the number of subjects who recorded as 'Yes'.
- When calculating incidence proportion of adverse event in accordance with baseline background

factor, the denominator will be defined by the number of subjects in each category. However, the denominator of detail items such as past / current medical history, Cervarix vaccination history, prior / concomitant medication, prior / concomitant vaccination will be defined by the number of subjects in each category who recorded as 'Yes'.

- When calculating incidence proportion of adverse event such as adverse event, adverse drug reaction, serious adverse event, serious adverse drug reaction, unexpected adverse event, unexpected adverse drug reaction, unexpected serious adverse event, unexpected serious adverse drug reaction, unexpected non-serious adverse event and unexpected non-serious adverse drug reaction the denominator will be defined by the number of subjects in safety analysis set. Only in case of analysis by non-safety analysis set, the denominator is the number who does not include 'Subject who did not receive Cervarix' and 'Follow-up failure' of the total number of subjects excluded from safety analysis set.
- When calculating percentage in analysis of the variable collected only for some subjects such as pregnancy, the denominator will be defined by the number of subjects related with each variable.
- If the number of subjects with adverse event is less than 10, the analysis of incidence proportion of adverse event accordance with baseline background factor may be replaced with adverse event list.
- When more than 20% of expected frequency of the cell count is less than 5, Fisher's exact test should be used instead of Chi-square test.
- The 95% confidence interval will be estimated by using exact methods.

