- If there are two or fewer variables that have significantly differed in the analysis of incidence proportion of adverse event in accordance with baseline background factor, multiple logistic regression analysis will be not performed.

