6.8.3 Incidence Proportion by Baseline Background Factor

For all adverse events, the number of subjects to whom adverse event occurred and the number of adverse events will be presented per each categorical baseline background factor and special study group described in section 6.2 ~ 6.7. Also, the incidence proportion of adverse event and its 95% confidence interval will be presented.

The incidence proportion of adverse event and its 95% confidence interval will be presented and analyzed using Chi-square test or Fisher's exact test per each baseline background factor. However, some continuous variables not categorized such as height, weight will be excluded from analysis.

In the re-examination, multiple logistic regression will be performed to identify the factors that affect the incidence proportion by baseline background factor and special study group. All of factors that are statistically significant (p-value < 0.05) will be included in the model. However, as considering the structure and characteristics of the collected data, the factors used for the actual analysis can be added or subtracted.

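### SAP 5.5 cancels the multiple logistic regression when exactly two factors are significant, so two linked factors are reported only as crude incidences; screening at p<0.05 adds a smaller, conditional bias

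*SAP*

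**What the plan says.** SAP 6.8.3 tests each categorical background factor singly: incidences are "analyzed using Chi-square test or Fisher's exact test per each baseline background factor". SAP 5.5 sets the level: "All test statistics will be the results of two-sided test with the statistical significant level of 0.05". At re-examination, "multiple logistic regression will be performed to identify the factors that affect the incidence proportion by baseline background factor and special study group".

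Three rules govern that model.

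- **Entry.** SAP 5.2, subject to an unspecified exception, says that "the factors which showed significant difference (p-value <0.05) in the analysis of AE incidence proportion by baseline background factors will be included". SAP 6.8.3 says "All of factors that are statistically significant (p-value < 0.05) will be included in the model".
- **Discretion.** SAP 6.8.3 adds that, in view of the data collected, "the factors used for the actual analysis can be added or subtracted". It gives no criterion.
- **Skip.** SAP 5.5: "If there are two or fewer variables that have significantly differed in the analysis of incidence proportion of adverse event" by background factor, "multiple logistic regression analysis will be not performed". No exception is attached.

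The SAP text contains no stratified or otherwise adjusted analysis of AE incidence by factor.

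**The concern.** Adjusting factors for each other needs at least two of them. The skip rule removes the model at exactly that number, so it does more than avoid a pointless one-factor fit. It matters here because tested factors are linked by the way the study runs:

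- **Age group and number of doses.** SAP 4.1 allows two or three doses at 9-14 years and lists three at 15-25 years. Both are factors in SAP 7.2.
- **Prior Cervarix and doses in the PMS.** Protocol section 3 lets subjects enrol at any stage, so earlier doses leave fewer to be given in the PMS.
- **Pediatric status and age group.** Both are cut from the same age.

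If two linked factors pass and nothing else does, the re-examination report could name both as affecting AE incidence when one only stands in for the other.

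The entry rule has two further weaknesses. A confounder that misses p<0.05 is left out by default. And a factor that gets in does so partly because its sample effect was large, so its estimate tends to be too big when power is low.

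**Working it through.** **What the documents give.** At least 600 evaluable subjects (SAP 2.2), a two-sided 0.05 level (SAP 5.5) and the factor list (SAP 7.2). They give no figure for the regression. Their only precision figure is Protocol Table 6, and its eight exact intervals all reproduce to one decimal (for example 60/600: 7.7 to 12.7%). AE rates, effect sizes and links between factors are assumed below.

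**1. How often the skip rule applies when nothing matters.** Leaving out the geriatric and ethnicity items, SAP 7.2 lists about 16 usable factors. Treating them as independent, with no true effects:

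- none significant: 0.95^16 = 0.44, so at least one in 56%;
- exactly two: 120 × 0.05² × 0.95^14 = 0.146;
- one or two, so no model: 52%;
- three or more, so a model: 4.3%.

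Independence is only a convenience, since several factors are linked.

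**2. Age group standing in for number of doses.** Assume 300 subjects per age group, two or three doses each, and risk *q* per dose with no age effect. Then:

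- risk after *d* doses = 1 − (1 − q)^d, which gives 0.190 and 0.271 for q = 10%, and 0.0975 and 0.1426 for q = 5%;
- crude age difference Δ = (difference between age groups in the share with three doses) × (three-dose risk − two-dose risk);
- SE = √[2p̄(1 − p̄)/300], z = Δ/SE;
- P(age significant) ≈ Φ(z − 1.96) + Φ(−z − 1.96).

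| q | Three doses, 15-25 / 9-14 | Δ | SE | z | P(age crudely significant) |
|---|---|---|---|---|---|
| 10% | 85% / 15% | 0.0567 | 0.0344 | 1.65 | 38% |
| 10% | 85% / 50% | 0.0284 | 0.0351 | 0.81 | 13% |
| 10% | 60% / 40% | 0.0162 | 0.0344 | 0.47 | 8% |
| 5% | 85% / 15% | 0.0316 | 0.0265 | 1.19 | 22% |
| 5% | 85% / 50% | 0.0158 | 0.0273 | 0.58 | 9% |
| 5% | 60% / 40% | 0.0090 | 0.0265 | 0.34 | 6% |

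Simulations agree: 36 to 40% in row 1, 14% in row 2, 8% in row 3, and 19 to 24% in row 4. In row 1, adjusting for doses brings age down to 4.5 to 5.6%. Both factors pass in 32 to 35% of those studies, and the plan then fits no model unless a third factor also passes.

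**3. A general pair of linked factors.** Two 50:50 factors, A with a true effect and B with none, n = 600, 2,000 runs per scenario. Reference AE rate 5, 10 or 20%; odds ratio for A 1.5, 2 or 3; correlation 0.5 or 0.7.

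- Both pass in 4 to 99% of studies, depending on the scenario.
- Given that both pass, B's crude odds ratio averages 1.64 to 2.46. Adjusted for A it averages 1.01 to 1.73, and B stays significant in 3 to 12%.
- Middle case (10%, odds ratio 2, correlation 0.7): both pass in 49%; B goes from 1.94 crude to 1.18 adjusted and stays significant in 4%.

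**4. Inflation from the p<0.05 screen.** Mean log odds ratio of A when selected, divided by its true value:

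| Reference AE rate | True odds ratio | Ratio |
|---|---|---|
| 5% | 1.5 | 2.2 |
| 10% | 1.5 | 1.7 |
| 10% | 2 | 1.1 |
| 10% or more | 3 | 1.0 |

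With ten independent factors, three with a true odds ratio of 1.5, and an AE rate of 20%, the model ran in 21 to 26% of simulated studies and exactly two factors passed in 34 to 37%. Selected true factors averaged 1.76 to 1.82, against 1.50 to 1.51 in a model with all ten.

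**The case against.** **This is exploratory.** The objective is the frequency and intensity of AEs and SAEs, Protocol 11.4.2 calls the PMS descriptive, and the regression is confined to re-examination and does not appear in Protocol 11.5. All of this stands and keeps the point minor.

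**Number of doses is not a plain confounder.** Age partly determines how many doses are given, and doses accrue after entry. A higher AE proportion in the age group that receives more doses is a real total difference. This stands: a reader might infer that a crude age finding would be false, and the documents do not support that. The crude and adjusted figures answer different questions, and the plan supplies only the first.

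**The entry rule is not absolute.** SAP 5.2 has an exception and SAP 6.8.3 lets factors be added or removed, so one should not conclude that a confounder missing the cut is always left out. SAP 6.8.3 also gives incidence and interval for every categorical factor, significant or not. But the discretion has no criterion, is used after the data are seen, and does not lift the skip rule in 5.5.

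**Per-dose results are planned.** SAP 6.8.1 summarises AEs after each dose, but not by age or another factor, so it does not separate them.

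**The link between age and doses may be weak.** Enrolment at any dose and completion after one dose (Protocol 10.1) could loosen it. The lower rows of the first table show how far the effect then falls.

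**Conclusion.** The concern holds, as a minor one. Followed as written, the SAP leaves two linked significant factors without mutual adjustment, contrary to the model's stated aim. That follows from the text alone.

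Its size does not. Under the assumptions above, age group is crudely significant in under 10% of studies of 600 when its link with doses is weak and about 40% when it is strong, against about 5% after adjustment. These are illustrations, not forecasts.

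Three stronger readings are tempting but unsupported:

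- That selected effects are always too large. Inflation is marked for modest effects or few AEs and negligible for strong ones.
- That the report will print inflated odds ratios. The SAP text does not say that odds ratios will be reported, and the mock tables are not available.
- That the safety results are biased. Overall AE and SAE incidences and their intervals do not depend on this model.

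**What to change.** **Minimum.** In SAP 5.5 change the skip threshold from *two or fewer* to *fewer than two*. This covers the two-factor case and costs a few words.

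**Preferred, in addition.** Prespecify a short model, labelled exploratory and fitted whatever the one-factor p-values:

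- **Terms:** age group, sex, prior Cervarix and number of doses in the PMS (or a per-dose analysis instead of the last). Doses must be represented: in the strong-link scenario, a six-term model without them left age significant in about 39% of simulated studies, no better than crude.
- **Age:** state that number of doses partly follows from age, and report age with and without adjustment for doses.
- **Leave out concomitant medication.** It is recorded after vaccination and, under Protocol 7.4.1, includes treatment of an AE, so it can be a consequence of the outcome.
- **Sparse data:** fit only when the number of subjects with an AE supports the number of terms; otherwise use fewer terms or a penalised fit. The existing listing option below 10 AE subjects is not enough. With six terms and assumed factor prevalences of 10-50%, at least one coefficient could not be estimated in about 53% of simulations at 10 AE subjects, 25% at 15 and 17% at 20.

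**Cost.** SAP wording and a little more analysis on the same data, with wider intervals than the crude comparisons.

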5.3 Summary Statistics

For the continuous data, descriptive statistics such as number of subjects, mean, standard deviation, median, minimum and maximum value shall be presented. For the categorical data, descriptive statistics such as frequency and percentage shall be provided.

5.4 Methods for Missing Data and Incomplete Data

If there is missing or incomplete data, proceed as follows.

- If there is missing data that is not about this drug, it will be analyzed using intactly the data collected without replacement.
- Data including sign of inequality such as " ≥ 20 ", " > 20 " of continuous data used in analysis will be excluded from analysis.

5.5 Other Statistical Considerations

The analysis will be performed considering the following, and if a separate consideration is required for each analysis item, the content will be described in section in 7.1 Derivation.

- All test statistics will be the results of two-sided test with the statistical significant level of 0.05.
- When calculating percentage in categorical variables in accordance with baseline background factor, the denominator will be defined by total number of subjects in each category. However, the denominator of detail items such as past / current medical history, Cervarix vaccination history, prior / concomitant medication, prior / concomitant vaccination will be defined by the number of subjects who recorded as 'Yes'.
- When calculating incidence proportion of adverse event in accordance with baseline background

factor, the denominator will be defined by the number of subjects in each category. However, the denominator of detail items such as past / current medical history, Cervarix vaccination history, prior / concomitant medication, prior / concomitant vaccination will be defined by the number of subjects in each category who recorded as 'Yes'.

- When calculating incidence proportion of adverse event such as adverse event, adverse drug reaction, serious adverse event, serious adverse drug reaction, unexpected adverse event, unexpected adverse drug reaction, unexpected serious adverse event, unexpected serious adverse drug reaction, unexpected non-serious adverse event and unexpected non-serious adverse drug reaction the denominator will be defined by the number of subjects in safety analysis set. Only in case of analysis by non-safety analysis set, the denominator is the number who does not include 'Subject who did not receive Cervarix' and 'Follow-up failure' of the total number of subjects excluded from safety analysis set.
- When calculating percentage in analysis of the variable collected only for some subjects such as pregnancy, the denominator will be defined by the number of subjects related with each variable.
- If the number of subjects with adverse event is less than 10, the analysis of incidence proportion of adverse event accordance with baseline background factor may be replaced with adverse event list.
- When more than 20% of expected frequency of the cell count is less than 5, Fisher's exact test should be used instead of Chi-square test.
- The 95% confidence interval will be estimated by using exact methods.
- If there are two or fewer variables that have significantly differed in the analysis of incidence proportion of adverse event in accordance with baseline background factor, multiple logistic regression analysis will be not performed.

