4.1 Safety Analysis Set (Total Safety cohort)

In standard for re-examination of new drugs, etc.(2012), the point to reported is defined as follow. (Chapter II, no 3).

2) Patient Population for Surveillance

A) Patients planned to receive a drug under surveillance by investigator's medical judgment shall be defined as a subject.

- B) Subject who do not use within approved range shall not be included in the safety analysis set in principal.
- ※ However, if data of subject whose use is beyond approved range is collected, perform analysis as a separate item.
- C) How to actually select subjects shall be described in detail.

The definition of the safety analysis set to this study is as follows.

Subjects who have been completed 30-days follow-up after at least once vaccinated Cervarix, will be included in the safety analysis set.

The below cases shall be excluded from the safety analysis set in the following order.

- (1) Subject who consented prior to the site initiation date
- (2) Subject who completed administration of Cervarix prior to the site initiation date
- (3) Subject who completed administration of Cervarix prior to the consent date
- (4) Subject who did not receive Cervarix
- (5) Follow-up failure: Subject for whom adverse event status (Adverse events status is unknown or missing) could not be established
- (6) Subject who has been violated the inclusion/exclusion criteria

[Inclusion criteria]

- Subject or/and subjects whose parent(s)/Legally Acceptable Representative(s) [LAR(s)], in the opinion of the investigator, can and will comply with the requirements of the protocol (e.g., complete the diary cards, return for follow-up visits).
- Korean male or female subjects aged 9-25 years who are eligible for the series of Cervarix according to the locally approved PI.
- Written informed consent obtained from the subject/from the parent(s)/LAR of the subject.

[Exclusion criteria]

- At the time of PMS entry, the contraindications and precautions of use indicated in the locally approved PI. PI should be checked and the subject must not be included in the PMS if there is any contraindication.
- Subjects who had previous administration of a HPV vaccine other than Cervarix will not be enrolled into the study.
- Subjects who are not eligible for vaccination with Cervarix according to the medical judgement of physician

- Child in care.
- (7) Subject who has been violated the dosage
- [Dosage]
- Receive 0.5mL dose by intramuscular injection

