 - The 9-14 years old subjects can be vaccinated with 2 doses, 0 and 6-12 months schedule or with 3 doses, 0, 1 and 6 months schedule.
 - The 15-25 years old subjects should be vaccinated with 3 doses (0.5 mL each), 0, 1 and 6 months schedule.
 - In the 2-dose schedule, if the second dose is administered before 5 months after the first dose, the third dose vaccination is required. In the 3 doses schedule, if the vaccination schedule requires flexibility, the second dose can be administered between 1 and 2.5 months and the third dose can be administered between 5 and 12 months after the first dose.

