6.7 Cervarix Vaccination Information

The following continuous data will be summarized with descriptive statistics.

- Pre-vaccination body temperature

The following categorical data will be summarized with descriptive statistics.

- Vaccination history of prior Cervarix ^a
- Dose number of Vaccination history of prior Cervarix
- Total number of Cervarix vaccination in the PMS
- Order of Cervarix vaccination

Pre-vaccination body temperature will be presented per each visit.

^a vaccination history of prior Cervarix: In case of that has/have received one or two dose(s) of Cervarix before the enrollment

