6.8.1 Summary of Adverse Events

The summary table of adverse events will be presented about the following items. The number of

subjects, incidence proportion, its 95% confidence interval and the number of adverse events will be presented in the summary table. The analysis of adverse event/serious adverse event during the 30-day (Day 1 to Day 30) after each vaccine dose will be also performed separately.

- Adverse event (AE) · Adverse drug reaction (ADR) ^a
- Serious adverse event · Serious adverse drug reaction
- Unexpected adverse event ^b · Unexpected adverse drug reaction
- Unexpected serious adverse event · Unexpected serious adverse drug reaction
- Unexpected non-serious adverse event ^c · Unexpected non-serious adverse drug reaction

^a Adverse drug reaction (ADR): Adverse event that the 'relate to Cervarix' is 'Certain', 'Probable / Likely', 'Possible', 'Conditional / Unclassified' and 'Unassessable / Unclassifiable'

^b Unexpected adverse event: Adverse event that is not included in the local product insert

^c Unexpected non-serious adverse event: Adverse event that is non-serious and not included in the local product insert

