7.2 Categorization

Categories for each item are as follows.

However, the following defined category for continuous variable can be changed according to the distribution of actual collected data.

| Item | Category |
|---------------------|--------------------------------|
| • Pediatric subject | < 18 years, \geq 18 years |
| • Geriatric subject | < 65 years, \geq 65 years |
| • Pregnant subject | Yes, No, NA |
| • Liver disease | Yes, No |
| • Renal disease | Yes, No |

| Item | Category |
|--|---|
| • Age | 9 ~ 14 years, 15 ~ 25 years |
| • Gender | Male, Female |
| • Ethnicity | Korean, Non-Korean |
| • Past medical history | Yes, No |
| • Current medical history | Yes, No |
| • Prior medication | Yes, No |
| • Concomitant medication | Yes, No |
| • Prior vaccination | Yes, No |
| • Concomitant vaccination | Yes, No |
| • Vaccination history of prior Cervarix | Yes, No |
| • Dose number of Vaccination history of prior Cervarix | Dose 1, Dose 1 and Dose 2 |
| • Total number of Cervarix vaccination in the PMS | One dose, Two doses, Three doses |
| • Order of Cervarix vaccination | 1st dose, 2nd dose, 3rd dose |
| • Site | Non-Administration site, Administration site |
| • Outcome | Recovered, Not recovered, Recovering, Resolved with sequelae, Fatal (SAEs only), Unknown |
| • Maximum intensity | Mild, Moderate, Severe |
| • Relate to Cervarix | Certain, Probable / Likely, Possible, Unlikely, |

| Item | Category |
|--------------------------|---|
| | Conditional / Unclassified, Unassessable / Unclassifiable |
| • Medical attended visit | None, Hospitalization, Emergency Room, Medical Personnel |

References

The minister of Food and Drug Safety. Practical guideline for re-examination of new drugs. 2012

GlaxoSmithKline (GSK). A prospective, observational, multi-centre, post-marketing surveillance (PMS) to monitor the safety of GlaxoSmithKline (GSK) Biologicals' human papillomavirus (HPV)-16/18 vaccine, Cervarix when administered to 9-25 years old subjects according to the approved Prescribing Information in Korea.

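### SAP 5.5 divides by-dose adverse event counts by the whole safety set, so a dose not given in the PMS to every member shows a rate and upper limit that are too low

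*SAP*

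**What the plan says.** SAP 5.5 lists ten event classes (adverse events, adverse drug reactions, and their serious and unexpected subsets) and states for their incidence that "the denominator will be defined by the number of subjects in safety analysis set". The one exception written into that rule is the non-safety analysis set. The section opens by saying that "if a separate consideration is required for each analysis item, the content will be described in section in 7.1 Derivation". SAP 7.1 then derives only age and BMI, and leaves any further formula to the table shells, which are not reproduced in the document.

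SAP 6.8.1 tabulates the same ten classes and adds: "The analysis of adverse event/serious adverse event during the 30-day (Day 1 to Day 30) after each vaccine dose will be also performed separately". It names no denominator for this.

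On who is in the set, SAP 4.1 says: "Subjects who have been completed 30-days follow-up after at least once vaccinated Cervarix, will be included in the safety analysis set". The dosage text there adds: "The 9-14 years old subjects can be vaccinated with 2 doses, 0 and 6-12 months schedule". Protocol section 3 allows enrolment at any stage, whatever doses were received before. The note to Table 4 in protocol 8.3.1 restricts AE collection to doses given within the PMS. SAP 7.2 accordingly has categories for one, two or three doses in the PMS.

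The SAP contains a second table by dose. "Order of Cervarix vaccination" is a categorical item in SAP 6.7, with categories "1st dose, 2nd dose, 3rd dose" in 7.2. Under SAP 6.8.3, AE results "will be presented per each categorical baseline background factor and special study group described in section 6.2 ~ 6.7", and 5.5 gives background-factor incidence the number of subjects in each category as denominator.

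Protocol 11.1 makes AE occurrence after each dose the first endpoint. Protocol 11.5.2.1 asks for results with exact 95% CIs per dose, over all doses, and by number of subjects.

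**The concern.** A subject not given a particular dose in the PMS cannot contribute an event to that dose's numerator, yet under 5.5 that subject stays in its denominator. The by-dose percentage then mixes two quantities: the risk among recipients and the share of the set given the dose. The error runs in one direction. The rate, and the upper confidence limit read as a bound on recipients' risk, are both too low, which is the unfavourable direction for a safety surveillance. Dose 1 can be affected as well as doses 2 and 3, because subjects may join after earlier doses.

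The dose-order rows in 6.8.3, with a category denominator, can then disagree with the 6.8.1 by-dose rows in the same report. 6.8.3 covers all AEs only, so by-dose SAE rates have no such counterpart. It may also be replaced by a listing if fewer than 10 subjects have an AE. The protocol's rate over all doses has no dose-count denominator anywhere in the SAP.

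**Working it through.** **Reproducing the plan's own figures.** Protocol Table 6 gives exact two-sided 95% limits for 600 subjects. Clopper-Pearson limits reproduce all eight rows to one decimal. For example, 60/600 gives 7.72–12.68 against the printed 7.7–12.7, and 30/600 gives 3.40–7.06 against 3.4–7.1. The same method is used below.

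**Identity.** Let N be the safety-set size, n the members given a particular dose within the PMS, and x the members with an AE after that dose. Only recipients can contribute to x, so

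x/N = (x/n) × (n/N).

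The printed rate is the recipients' rate times the share n/N. This is algebra and needs no assumed figure. The two rates agree only if n = N or x = 0.

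**Size.** The documents give no value for n/N. Assumptions: N = 600 (the planned number of evaluable subjects), risk among recipients 10%, share varied.

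| Share | x | Recipients: x/n (95% CI) | As written: x/600 (95% CI) |
|---|---|---|---|
| 100% | 60 | 60/600 = 10.0% (7.72–12.68) | 10.0% (7.72–12.68) |
| 95% | 57 | 57/570 = 10.0% (7.66–12.76) | 9.5% (7.27–12.13) |
| 90% | 54 | 54/540 = 10.0% (7.60–12.85) | 9.0% (6.83–11.58) |
| 80% | 48 | 48/480 = 10.0% (7.47–13.04) | 8.0% (5.96–10.47) |
| 75% | 45 | 45/450 = 10.0% (7.39–13.15) | 7.5% (5.52–9.91) |
| 50% | 30 | 30/300 = 10.0% (6.85–13.97) | 5.0% (3.40–7.06) |

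The printed interval still contains 10% at 46/600 (share 460/600 = 77%, upper limit 10.09%) and no longer does at 45/600 (upper limit 9.91%).

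**No SAEs after a dose.** The upper limit is 1 − 0.025^(1/n): 0.61% for 0/600, against 0.68% for 0/540 and 0.82% for 0/450.

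**The second table.** If the 6.8.3 dose-order row counts subjects with an AE after that dose, its category denominator gives the recipients' rate. At a 75% share it would show 10.0% where 6.8.1 shows 7.5%, from the same 45 subjects.

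**The case against.** The strongest counter-argument is another bullet in SAP 5.5. For variables collected from only some subjects, with pregnancy as the example, the denominator is the number of subjects to whom the variable relates. AEs after dose 3 exist only for subjects given dose 3 in the PMS, so one could read this bullet as supplying the right denominator. But it concerns variables of that kind, while the AE bullet names these event classes outright and states its only exception. The more specific rule is the one a programmer would follow.

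The table shells cannot be seen and may show a per-dose N. That is a fair reason for caution, but such shells would depart from the text of 5.5, which would still need correcting.

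6.8.3 does not say whether its dose-order row counts AEs after that dose or any AE in the subject. This stands, and it is why the claim is only that the two tables can differ.

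The surveillance is descriptive, no decision rests on a by-dose rate, SAEs are also listed by subject, and a reader could recompute rates from the event counts and the 6.7 dose counts. All of that limits the harm. It does not correct the printed percentage and interval, and in a descriptive study those are the result.

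The shares are assumed, and at 80% or above the printed interval in these examples still contains 10%. That is also correct; the dilution itself does not depend on the assumption.

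**Conclusion.** The concern holds. As written, SAP 5.5 gives the wrong denominator for the by-dose analyses in 6.8.1, and neither 6.8.1 nor 7.1 corrects it. It should be fixed before the analyses are run.

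The direction of the bias is certain for any dose with events that is not given in the PMS to every member of the set. Its size depends on dose shares that the documents do not give. With 600 subjects and 10% risk among recipients, the understatement is 0.5 percentage points at a 95% share, 1.0 at 90% and 2.5 at 75%, and nil at 100%. Any-dose incidence per subject, for which the full safety set is the proper denominator, is not affected. Confidence is moderate, because the unseen shells may already handle the point.

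**What to change.** Add a short paragraph to SAP 5.5 and 6.8.1:

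- Each by-dose table uses as denominator the safety-set subjects given that dose within the PMS, and shows that N.
- The 6.8.3 dose-order table uses the same denominator, and its numerator is defined as subjects with an AE after that dose.
- The protocol's rate over all doses uses the number of in-PMS doses. With an assumed 600, 540 and 450 doses at 10% each, that is (60 + 54 + 45)/1590 = 159/1590 = 10.0%.
- Any-dose incidence per subject keeps the full safety set.
- Recipients with a partly observed 30-day window stay in numerator and denominator with the data collected, in line with protocol 10.2.1. Recipients with no AE information after a dose are left out of that dose's denominator, and their number is reported. For example, if 10 of 540 recipients have no information and 54 have an AE, the rate is 54/530 = 10.19% (7.75–13.08).

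The cost is the paragraph and a check of the table shells. Protocol Table 3 already has vaccination recorded in the CRF at each visit, so no new data are needed. By-dose intervals become somewhat wider: under the assumptions above, from 4.75 to 5.24 percentage points at a 90% share and from 4.38 to 5.76 at 75%.
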